### **10.4.4 Quality Assurance**

The Principal investigator will be responsible for ensuring that informed consent is properly obtained and that adverse events and protocol violations are reported to the Partners IRB as required.

### **10.4.5 E-Health App Privacy and Security**

See Appendix 4 for the specifications related to the e-Health App which will be used for this study.

## **10.5 Adverse Experiences Monitoring and Reporting**

An adverse event (AE) is any unfavorable and unintended sign (including a clinically significant abnormal laboratory finding, for example), symptom, or disease temporally associated with a study, use of a drug product or device whether or not considered related to the drug product or device.

The adverse event (AE) definitions and reporting procedures provided in this protocol comply with all applicable U.S. FDA and ICH guidelines and regulations. The Principal Investigator will carefully monitor each subject throughout the study for possible adverse events. All AEs will be documented on eCRFs designed specifically for this purpose. It is also important to report all AEs, especially those that result in permanent discontinuation of the investigational drug being studied, whether serious or non-serious.

Subjects will be monitored for adverse events from the time they sign consent until completion of their participation in the study. For the purposes of this study, symptoms of progression/worsening of ALS, PD and HD including ‘normal’ progression, will not be recorded as adverse events. Relationship of adverse experiences to the experimental intervention will be assessed at each in-person and telephone study visit by recording all voluntary complaints of subjects and by assessment of the medical. Attention will be directed to clinical adverse experiences associated with the prior hypercaloric dietary intervention, as well as any evidence of unexpected worsening of the underlying disease. Laboratory surveillance tests will be obtained as outlined above.

A serious adverse event is defined as an adverse event that meets any of the following criteria:

- Results in death
- Is life threatening: that is, poses an immediate risk of death as the event occurred. This serious criterion applies if the study subject, in the view of the Site Investigator, is at substantial risk of dying from the AE as it occurs. It does not apply if an AE hypothetically might have caused death if it were more severe.
- Requires inpatient hospitalization or prolongation of existing hospitalization. Hospitalization for an elective procedure (including planned tracheostomy) or a routinely scheduled treatment is not an SAE by this criterion because a “procedure” or a “treatment” is not an untoward medical occurrence.
- Results in persistent or significant disability or incapacity. This serious criterion applies if the “disability” caused by the reported AE results in a substantial disruption of the subjects’ ability to carry out normal life functions.
- Results in congenital anomaly or birth defect in the offspring of the subject (whether the subject is male or female)
- Necessitates medical or surgical intervention to preclude permanent impairment of a body function or permanent damage to a body structure.

An event is considered “life-threatening” if it places the subject, in the view of the Investigator, at immediate risk of death from the reaction as it occurred; i.e., it does not include a reaction that, had it occurred in a more severe form, might have caused death.

Important medical events that may not result in death, are not life-threatening, or do not require hospitalization may also be considered SAEs when, based upon appropriate medical judgment, they may jeopardize the subject and may require medical or surgical intervention to prevent one

of the outcomes listed in this definition. Examples of such medical events include blood dyscrasias or convulsions that do not result in inpatient hospitalization, or the development of drug dependency or drug abuse.

An inpatient hospital admission in the absence of a precipitating, treatment-emergent, clinical adverse event may meet criteria for "seriousness" but is not an adverse experience, and will therefore, not be considered an SAE. An example of this would include a social admission (subject admitted for other reasons than medical, e.g., lives far from the hospital, has no place to sleep).

An unexpected adverse event is any adverse event, the specificity or severity of which is not consistent with expected risks of the study intervention.

All unexpected and related SAEs will be reported to the Partners IRB within 24 hours of being aware of the event. Death due to progression of disease, as expected in ALS, will not be reported in an expedited manner except in cases where the outcome of death is deemed related to study treatment.

There will be ongoing monitoring of non-serious Adverse Experiences. All AEs will be summarized and reported to the Medical Monitor on a monthly basis.

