### **4.4.2 Randomization Process**

Randomization of sites will be performed independently by the MGH Biostatistical center using a computer-generated system. Randomization will be stratified by disease group and by the presence or absence of weight loss at baseline (i.e., a decline of 5% of body weight from the time of first symptoms by self-report). Each participant will receive a unique ID number (see section 10.4.1) for data entry. This unique ID will also be used to identify the subject's Source Documents, electronic case report forms (eCRFs), and all communications. The unique ID will also be used to link the study data to the e-Health App data by having participants enter their unique ID into the e-Health App system when creating their username. Due to the design of the study, participants and evaluators cannot be blinded to treatment assignments.

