## **6.2 Definitions of Evaluations and Outcome Measures**

### **6.2.1 Primary Outcome Measures**

#### **6.2.1.1 Safety and Tolerability**

Safety will be evaluated using reporting of hospitalizations, deaths and other serious adverse events, and treatment discontinuations due to adverse events. Tolerability will be defined as the number of participants who do not decline nutritional counseling, i.e. the number of participants who complete the 6 months of counseling sessions in the in-person arm, or who enter at least 80% of the required data in the e-Health application arm. Tolerability will not be defined based on compliance with nutritional recommendations as compliance may be affected by other factors such as disease progression.

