## **7. Adverse Experiences Related to Medical Nutrition Therapy**

### ***Weight gain***

An increase in weight in either of the intervention arms is expected and would not be considered an adverse event. In the High-Fat/High Calorie versus Optimal Nutrition in ALS clinical trial, there were no complications of heart disease, diabetes, or breathing problems in the study arms who received hypercaloric diets. Increase in weight was seen in the high-carbohydrate hypercaloric arm and was associated with fewer AE and SAE. We will therefore tell participants that they are expected to gain weight and that we will not consider this an adverse event.

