	SAE	0	0 (0)	0	0 (0)	1	1 (17)	0.6	>0.99	>0.99	0.6	>0.99	>0.99
Pain (Abdomin, neck, limb)	AE	3	2 (33)	2	2 (25)	4	3 (50)	0.58	0.46	0.72	0.84	>0.99	>0.99
	SAE	2	1 (17)	0	0 (0)	0	0 (0)	0.18	0.18	0.5	0.6	0.43	>0.99
Pulmonary/Upper Respiratory (Dyspnea, hypoxia, aspiration, cough)	AE	8	3 (50)	1	1 (13)	6	3 (50)	0.16	0.075	0.72	0.28	0.24	>0.99
	SAE	6	3 (50)	0	0 (0)	2	2 (33)	0.007	0.006	0.29	0.07	0.06	>0.99
Total	AE	42	6 (100)	23	8 (100)	48	6 (100)	0.06	0.06	0.73	>0.99	>0.99	>0.99
	SAE	9	4 (67)	0	0 (0)	3	3 (50)	<0.001	<0.001	0.15	0.03	0.015	>0.99

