If discernible at the time of completing the AE log entry, a specific disease or syndrome rather than individual associated signs and symptoms should be identified by the Site Investigator and recorded on the AE log. However, if an observed or reported sign, symptom, or clinically significant laboratory anomaly is not considered by the Site Investigator to be a component of a specific disease or syndrome, then it should be recorded as a separate AE on the AE log. Clinically significant laboratory abnormalities are those that are identified as such by the Site Investigator and/or those that require intervention. The only exception to this will be disease progression symptoms as previously noted.

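### The adverse-event rule excludes all symptoms of disease worsening, so non-fatal hospitalizations attributed to progression, and unexpected worsening, can drop out of an unblinded primary safety comparison

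*Protocol*

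**What the plan says.** Protocol section 10.5 sets the exclusion: "For the purposes of this study, symptoms of progression/worsening of ALS, PD and HD including" normal "progression, will not be recorded as adverse events". Section 10.5.1, on what goes into the AE log, carries it forward: "The only exception to this will be disease progression symptoms as previously noted".

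The same paragraph of 10.5 directs attention to events associated with the earlier hypercaloric diet, "as well as any evidence of unexpected worsening of the underlying disease".

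Section 10.5 defines an SAE as an AE that meets a seriousness criterion. It adds that an admission with no precipitating clinical AE is not an SAE.

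Section 6.2.1.1, under the primary outcome measures, states: "Safety will be evaluated using reporting of hospitalizations, deaths and other serious adverse events, and treatment discontinuations due to adverse events". Section 9.1 and the SAP compare AE totals by negative binomial regression and the proportion with each event type by Fisher's exact test. The SAP does not mention the progression exclusion.

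On blinding, section 4.4.2 says that "participants and evaluators cannot be blinded to treatment assignments".

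Section 7 describes the prior trial thus: "there were no complications of heart disease, diabetes, or breathing problems in the study arms who received hypercaloric diets".

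**The concern.** The word linking the two halves of the exclusion makes normal progression one example of what is left out, not its limit. Abnormal or faster worsening is therefore covered by the bar, although staff are told to look for it. No section says where such worsening is entered or how it is told apart from excluded progression.

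The effect reaches the primary safety outcome, because the SAE definition hangs on the AE definition. If an ALS patient is admitted with breathing difficulty and the cause is put down to progression, there is no AE. On the plan's own definition there is then no SAE. Section 6.2.1.1 nevertheless lists hospitalizations as part of the outcome.

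The call is made with the arm known. If the labelling threshold differs by arm, the AE and SAE comparison is biased. If it does not differ, the comparison still loses events. An event that was never entered cannot be restored by any analysis, and the Medical Monitor sees only what was recorded.

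**Working it through.** **1. Path of a non-fatal admission attributed to progression.**

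- 10.5 and 10.5.1: symptoms of progression or worsening are not logged, so there is no AE.
- 10.5: an SAE is an AE that meets a criterion, so there is no SAE.
- 10.5: an admission without a precipitating AE is not an SAE. The example given is a social admission, so the clause may have been meant narrowly, but the definition in the previous line already gives this result.
- 6.2.1.1: hospitalizations are part of primary safety. Its wording treats them as a kind of SAE, so it does not clearly bring the admission back.

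These sections leave open whether the admission counts.

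**2. Check of the prior-trial table (Table 3, section 7).** Arms are control / HC/HC / HF/HC. The rows sum to the printed totals: AEs 42 + 23 + 48 = 113 and SAEs 9 + 0 + 3 = 12. (Section 2.1.7 gives 24 and 49 AEs for the two hypercaloric arms. This is a small mismatch that does not matter here.) The printed p-value for any SAE, HC/HC against control, is 0.015. For 4/6 against 0/8, Fisher's test gives C(6,4)/C(14,4) = 15/1001 = 0.015, which reproduces it.

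**3. Upper bound on relabelling.** The row is "Pulmonary/Upper Respiratory (Dyspnea, hypoxia, aspiration, cough").

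- AEs: 8 + 1 + 6 = 15, and 15/113 = 13%.
- SAEs: 6 + 0 + 2 = 8, and 8/12 = 67%.
- Hypercaloric arms alone: 1 + 6 = 7 AEs and 0 + 2 = 2 SAEs.
- Controls alone: 8 AEs and 6 SAEs.

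**4. What removing that row would do.** SAEs go from 9/0/3 to 3/0/1. Table 3 leaves 1 or 2 controls with a non-pulmonary SAE. The any-SAE test of HC/HC against control becomes:

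- 2/6 against 0/8: C(6,2)/C(14,2) = 15/91, p = 0.16
- 1/6 against 0/8: 6/14, p = 0.43

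In that trial, relabelling would have hidden an apparent benefit.

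**5. Differential labelling (assumed fractions).** Let m1 and m0 be the shares of overlapping events called progression in the intervention and standard-care arms. Then observed ratio = true ratio × (1 − m1)/(1 − m0).

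| m1 | m0 | True ratio | Observed ratio |
|---|---|---|---|
| 0.50 | 0.25 | 1.0 | 0.67 |
| 0.50 | 0.25 | 1.5 | 1.00 |
| 0.50 | 0.25 | 2.0 | 1.33 |
| 0.50 | 0.50 | 1.5 | 1.50, with half the events lost |

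Reversing the first pair (0.25 and 0.50) turns a true ratio of 1.0 into 0.75/0.50 = 1.5. The direction is not fixed.

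**6. How far the mortality rule covers the gap.** Section 9.5 compares death or permanent assisted ventilation by logrank, at a cumulative one-sided 0.0574 per arm. Assume 50 per arm (150/3), the 23% annual mortality of section 9.3, 6 months of follow-up, no dropout and no interim looks.

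- Six-month risk: 1 − 0.77^0.5 = 0.1225, so about 6.1 deaths per arm if there is no effect.
- Power = Φ(√d/2 × ln HR − 1.577), where d is the total number of deaths.

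| HR | d | Power |
|---|---|---|
| 1.5 | 15.0 | 21% |
| 2 | 17.6 | 45% |
| 3 | 22.3 | 85% |

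Dropout lowers these figures and longer follow-up raises them. The rule is not designed to detect non-fatal harm.

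**The case against.** Keeping expected decline out of the AE log is a defensible way to limit noise in these diseases, and open-label conduct is unavoidable with counselling arms. Several stronger readings are tempting, and the documents do not support them.

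- A reader might infer that deaths vanish. They do not. Section 10.5 withholds only expedited reporting of progression deaths. Survival (6.2.3.1) and the stopping rule (9.5) count death and permanent assisted ventilation whatever the cause.
- A reader might infer that worsening leaves no trace. Disease rating scales, swallow rescreening, feeding-tube dates and reasons for discontinuation are all collected. They do not restore events to the AE or SAE counts, but a harm acting through decline or swallowing would show somewhere.
- A reader might infer that hypercarbia would go unseen. Section 2.2.2 presents it as an earlier hypothesis, measured by serum bicarbonate, with 3 control cases and none in the hypercaloric arms. Basic chemistry is repeated at clinic visits, although its components are not listed, and a clinically significant laboratory abnormality is an AE.
- A reader might add falls, weakness, fatigue and weight change to the pulmonary row and conclude that 38 of 113 AEs (34%) would be lost. That supposes every such event is relabelled. The rule covers symptoms of progression, and 10.5.1 asks for a specific disease to be logged where one can be identified, so a pneumonia is not plainly excluded.
- A reader might say that the plan hands the progression call to unblinded investigators. That is an inference from 10.5.1, where the Site Investigator judges what belongs to a syndrome and the Principal Investigator evaluates AEs. No section assigns the call expressly.

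What stands after this is narrower. The exclusion is broader than normal progression, unexpected worsening has no AE route, and sections 6.2.1.1 and 10.5 do not agree on non-fatal admissions.

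**Conclusion.** The point holds for non-fatal hospitalizations attributed to progression, other non-fatal events that meet a seriousness criterion, and unexpected worsening. Followed as written, the plan can leave these out of a primary outcome in a trial where evaluators know the arm and no blinded adjudication is described.

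The size cannot be fixed from the documents. The prior trial gives only an upper bound: 8 of 12 SAEs and 15 of 113 AEs were of the kind most easily read as ALS progression. Six of those 8 SAEs were in controls, so the figures are not evidence that the diet does harm, and relabelling could hide a benefit as easily as a harm. The labelling fractions in the working are assumptions chosen to show the mechanism.

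Separately, the section 7 statement that the hypercaloric arms had no breathing problems does not match Table 3, which lists 7 pulmonary AEs and 2 pulmonary SAEs in those arms. This is a correction to background text and does not bear on whether the recording rule is right.

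**What to change.** In sections 10.5 and 10.5.1:

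- Limit the exclusion to non-serious symptoms of expected progression, and say what makes worsening unexpected.
- Record every hospitalization, every death, every other event meeting a seriousness criterion and any unexpected worsening as an AE or SAE, whatever the suspected cause.
- Add one yes/no eCRF field: consistent with expected disease progression.

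In section 9.1 and the SAP, compare SAEs between arms with all events as the main analysis and with flagged events removed as supportive.

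Reconcile 6.2.1.1 with 10.5 and 10.5.1, so that it is clear that a hospitalization counts whatever its attribution. Correct the section 7 sentence to agree with Table 3.

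The cost is protocol and SAP wording, one eCRF field and additional disease-related entries in all arms. Logging every non-serious respiratory event, fall or metabolic event as well would go further, but it is more debatable and is not needed to close this gap.

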### **10.5.1 Evaluating and Recording of Adverse Events**

At each visit all adverse events that are observed, elicited by the Principal Investigator, or reported by the subject will be recorded in the appropriate section of the Adverse Event log, entered into the EDC and evaluated by the Principal Investigator.

Adverse events will be categorized according to the MedDRA coding system. This is a descriptive terminology, organized by body system and including specific criteria for grading severity of Adverse Events. This system will allow study coordinators to quickly search for the most relevant term for each event and will give specific criteria governing the reporting of severity for each term. With this system, the event will be coded at the site and subsequently checked by the Data Manager.

Minimum information required for each AE includes type of event, duration (start and end dates), severity, seriousness, causality to study intervention, action taken, and outcome.

---

The relationship of the AE to the study intervention should be specified by the Site Investigator, using the following definitions:

1. Not Related: Concomitant illness, accident or event with no reasonable association with treatment.
2. Unlikely: The reaction has little or no temporal sequence from administration of the study intervention, and/or a more likely alternative etiology exists.
3. Possibly Related: The reaction follows a reasonably temporal sequence from administration of the intervention and follows a known response pattern to the suspected intervention; the reaction could have been produced by the study

intervention or could have been produced by the volunteer's clinical state or by other modes of therapy administered to the volunteer.

4. **Probably Related:** The reaction follows a reasonable temporal sequence from administration of study intervention; is confirmed by discontinuation of the study intervention or by rechallenge; and cannot be reasonably explained by the known characteristics of the volunteer's clinical state.
5. **Definitely Related:** The reaction follows a reasonable temporal sequence from administration of study medication; that follows a known or expected response pattern to the study medication; and that is confirmed by improvement on stopping or reducing the dosage of the study medication, and reappearance of the reaction on repeated exposure.

---

If discernible at the time of completing the AE log entry, a specific disease or syndrome rather than individual associated signs and symptoms should be identified by the Site Investigator and recorded on the AE log. However, if an observed or reported sign, symptom, or clinically significant laboratory anomaly is not considered by the Site Investigator to be a component of a specific disease or syndrome, then it should be recorded as a separate AE on the AE log. Clinically significant laboratory abnormalities are those that are identified as such by the Site Investigator and/or those that require intervention. The only exception to this will be disease progression symptoms as previously noted.

## **11 HUMAN SUBJECTS**

### **11.1 Institutional Review Board (IRB) Review and Informed Consent**

The PI will obtain approval from the Partners Human Research Committee (HRC, or Partners IRB) of this protocol and consent form. Signed consent will be obtained from each subject. The consent form will describe the purpose of the study, the procedures to be followed, and the risks and benefits of participation. A copy of the consent form will be given to the subject, and this will be documented.

The PI and all key personnel involved in the study will have completed the Collaborative IRB training initiative, a mandatory tutorial on the responsible conduct of human subject research, or will have completed a comparable, institution-approved tutorial regarding the protection of human subjects. An independent Medical Monitor will review the study data for safety concerns. The PI will be responsible to report adverse events experienced by study subjects to the MGH IRB, the Medical Monitor, and if requested the study sponsor.

### **11.2 Subject Confidentiality**

Confidentiality will be maintained, as all subject research data will be coded with GUID number and initials. Blood samples for research will be de-identified and labeled using the GUID, prior to storage. Participant files will be kept in a secure, double-locked area. The electronic database used during the trial will be secure. To date no breach of our security barriers has occurred, and we actively maintain a high level of security to assess the confidentiality of our databases. Only key personnel in this proposal will have access to the data and the codes. Subject results will never be discussed in any form in the presence of other subjects in the study or with non-laboratory personnel. A subject will be referred to by his/her GUID number only. The PI, Steering Committee, and independent Medical Monitor will monitor privacy and confidentiality throughout the study.

### **11.3 Inclusion of Women**

The gender distribution for subjects with sporadic ALS is approximately 60% male and 40% female. The MGH patient population includes 53% men and 47% women. The gender distribution for PD is approximately 66% to 33% while the gender distribution in HD is 50% to 50%. [name] own clinic population is approximately 60% female. The study goal is to recruit men and women with ALS, PD and HD in an approximately equal ratio. Advertising the study with several disease foundations and patient support groups will aid in the recruitment process and, in particular, with the recruitment of female subjects.

